#### 10.4.2 Analysis of Secondary Endpoint

Clinical success rate at 12 months will be summarized using frequency (N) and percentage (%). The same type of analysis described for the primary endpoint will be carried out on this secondary endpoint. This analysis will use the PP population as the primary analysis population and the SAF population for sensitivity analysis.

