2 STUDY OBJECTIVES

2.1 Primary Objective(s)

The primary objective of this study is to assess safety and performance of the MINITAC[◇] Ti 2.0 Suture Anchor in extremities over a time period of 6 months after intervention.

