2.2 Secondary Objective(s)

The secondary objective of this study is to assess safety and performance of the MINITAC[◇] Ti 2.0 Suture Anchor in extremities over a time period of 12 months after intervention.

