5.3.3 Analysis of the Secondary Endpoint

The proportion of subjects with clinical success at 12 months post operation (365 days + 30 / - 150 days) will be summarized with a frequency and percentage. . As with the primary endpoint, subgroup (defined in section 3.3) corresponding proportions will be presented in tabular form. .

Incidence rates of the post-operative device failure and/or device related re-intervention at 12 months will be estimated as described above for the analysis of the primary endpoint.

Time to the first case of postoperative device failure and/or device-related re-intervention from operation date will be analyzed using the Kaplan-Meier method to estimate median time and related 25th and 75th percentiles. Patients without postoperative device failure or device related re-intervention will be censored at the latest date of assessment based on CRF data or date of death, whichever is earlier.

A by-subject listing of clinical success status will be provided for all subjects in the safety population. The listing will include subject identifier, date of 6-month visit, date of 12-months visit, clinical success status at 6-month visit or 12-month visit, date of device failure, description of failure, date of re-intervention, reason of re-intervention, and other information.

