5.8 Changes in the Conduct of the Planned Analysis

The following are changes from the protocol in the conduct of the planned analyses:

- In the protocol section 10.1, it is mentioned that generally all significance tests will be two-sided, performed at the 5% significance level, and resulting p-values will be quoted. However, for this study, given the small convenience study sample, the nature of non-intervention, as well as the absence of a priori statistical hypotheses, no formal hypothesis tests of statistical significance are planned, and as such, no p-values will be calculated. Relatedly, since statistical intervals are based on the same statistical assumptions as p values, no 95% confidence intervals will be estimated;
- The study will not employ separate safety and per protocol analysis sets. Instead, only one analysis set, the FAS as defined above, will be employed for all analyses;
- Kaplan-Meier estimation will not be used to estimate the event rate of postoperative device failure and/or device-related re-intervention at both 6 and 12-months. Instead incidence rates crude and model estimated incidence rates will be calculated;
- An analysis of the primary endpoint is included here +/- 3 months (3-9 month window) as per standard of care.

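### Kaplan-Meier for device failure or re-intervention is limited to quartiles that will rarely be reached, and person-time for the incidence rates is not tied to one definition

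*SAP*

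**What the plan says.** SAP 5.3.3 plans a time-to-event analysis of first postoperative device failure and/or device-related re-intervention, counted from the operation date. It "will be analyzed using the Kaplan-Meier method to estimate median time and related 25th and 75th percentiles". Patients without an event "will be censored at the latest date of assessment based on CRF data or date of death, whichever is earlier". No other Kaplan-Meier output is named.

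SAP 5.8 states: "Kaplan-Meier estimation will not be used to estimate the event rate of postoperative device failure and/or device-related re-intervention at both 6 and 12-months". It continues: "Instead incidence rates crude and model estimated incidence rates will be calculated". The list containing this bullet opens with "The following are changes from the protocol in the conduct of the planned analyses". Protocol 10.4, however, has no Kaplan-Meier analysis. Section 10.4.1 gives a frequency, a percentage and an exact interval, and 10.4.2 adds only that "The same type of analysis described for the primary endpoint will be carried out on this secondary endpoint". The quartile analysis that SAP 5.3.3 introduces is not listed in 5.8.

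For the incidence rates, SAP 5.3.2 defines person-months for each patient as running from baseline to 6 months. The Poisson offset is the log of each patient's time at risk. Patients with events and numbers of events are both tabulated, without saying which is the numerator. SAP 5.3.3 carries the method to 12 months by cross-reference.

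**The concern.** A Kaplan-Meier quantile exists only once the curve has fallen far enough: to 75% event-free for the 25th percentile and to 50% for the median. If about one patient in twenty fails, those table cells will nearly always read as not estimable. The same dates give the estimated probability of being event-free at 6 and at 12 months. That statistic suits objectives framed "over a time period of 6 months after intervention" and "over a time period of 12 months after intervention", and it is the one that SAP 5.8 rules out. The incidence rates that stay are per person-month, not probabilities at a time point.

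The second issue is that a crude rate and a Poisson rate built on different person-time would divide the same events by different denominators. If person-months are read literally, patients last seen early are credited with time in which nobody observed them, and the rate comes out too low.

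**Working it through.** **Inputs.** SAP 5.7: 95% success, N = 30 to 50. SAP 5.3.2 and 5.3.3: the chart windows are days 182−150 = 32 to 182+30 = 212, and 365−150 = 215 to 365+30 = 395. The documents give no separate rate for device failure or re-intervention, so 5% failure is taken from the 95%. They attach no time point to it, so both day 365 and day 182 are tried. Constant hazard and the contact patterns below are assumptions.

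**The plan's own figure.** At p = 0.95, the chance that the exact 95% interval has a half-width of at most 0.10:
- N = 30 needs at least 29 successes: 0.95^30 + 30 × 0.05 × 0.95^29 = 0.2146 + 0.3389 = 0.5535.
- N = 50 needs at least 44 successes: 0.9882.

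These match the stated 55.4% and 98.8%, so 5% failure is the working planning value.

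**Quantiles, full follow-up.** The 25th percentile needs 8 of 30 events (22/30 = 0.733 ≤ 0.75) or 13 of 50 (37/50 = 0.74). The chance is the binomial tail P(X ≥ k).

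| Failure risk | N = 30 | N = 50 |
|---|---|---|
| 5% | 8.5 × 10⁻⁵ | 7.5 × 10⁻⁷ |
| 10% | 0.8% | 0.1% |
| 20% | 23.9% | 18.6% |

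The median needs 15 of 30 or 25 of 50 events: 2.3 × 10⁻¹² and 1.1 × 10⁻¹⁹ at 5%.

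**Quantiles, staggered last contacts.** Simulated, with at least 15,000 studies per row and censoring independent of outcome. If the 5% refers to day 182, the risk by day 365 is 1 − 0.95^(365/182) = 9.8%. Ranges are differences between runs.

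| 5% failure by | Last contact | 25th percentile reached, N = 30 | N = 50 |
|---|---|---|---|
| day 365 | evenly over days 215–395 | 1.2% | 0.7% |
| day 365 | half over 32–212, half over 215–395 | 2.2% | 1.4% |
| day 182 | evenly over days 215–395 | 4.4–4.5% | 2.5–2.7% |
| day 182 | half over 32–212, half over 215–395 | 7.0–7.1% | 4.8% |

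Heavier early loss (80% last seen over days 32–212) gives 4.0% and 2.9% at 5% by day 365. At 10% by day 365 it gives 10.0% and 7.7%. In the day-365 rows of the table the median is reached in at most about 0.5% of studies. Where a quantile is reached, it is mainly through a late event in a very small risk set.

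**Landmark probabilities from the same curve.** 5% by day 365, contacts over days 215–395, censoring independent of outcome:
- Day 182: mean 97.5%, SD 2.9 points (N = 30) or 2.2 (N = 50).
- Day 365: mean 95.0%, SD 5.0 or 3.8. About 5 of 30 or 8 of 50 are still at risk.

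**Person-time.** An intercept-only Poisson model with a log person-time offset returns events divided by person-time. For example, 28 patients at 6 months plus one at 2 and one at 3 give 173 months. Two events give 2/173 = 0.01156 per month from both methods. Crediting all 30 patients with 6 months gives 2/180 = 0.01111. So, with no covariates, the two rates can differ only through person-time or through which events are counted.

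For contacts spread evenly over days 32–212, mean observed time up to day 182 is [(182² − 32²)/2 + 30 × 182]/180 = (16,050 + 5,460)/180 = 119.5 days. Understatement if everyone is credited 182 days:
- nobody seen after day 212 (extreme): 1 − 119.5/182 = 34%;
- half have later notes: 1 − 150.75/182 = 17%;
- 80% have later notes: 1 − 169.5/182 = 7%.

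**The case against.** **The endpoints are already covered.** Both objectives are tied to clinical success, planned as a percentage at 6 and 12 months beside incidence rates and by-subject listings with failure and re-intervention dates. A reader might infer that the objectives go unanswered, or that SAP 5.3.3 and 5.8 contradict each other. Neither follows. The Kaplan-Meier analysis is supplementary and concerns a different event. The two sections address different outputs of the curve, and 5.8 declares its choice and names a replacement. This stands and limits the point to a poor choice of supplementary statistic.

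**The planning rate is not firm.** The 5% has no time point, and the protocol's definition of success is close to the Kaplan-Meier event, so 5% cannot be treated as a ceiling. This stands, hence the rows for day 182.

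**Landmark estimates can be biased.** The means above rest on censoring unrelated to outcome. In chart review, failures may return while well patients stop attending. If every failure is charted and all others are censored at last contact, the day-365 estimate averages about 93%, or about 88% with half last seen early, against a true 95%. The 25th percentile would then be reached, spuriously, in 12–25% of studies. This stands and has to be stated with the estimate, but the planned quantiles carry the same weakness.

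**The two person-time wordings may mean one quantity.** They may, and a common end at 6 months is stated. What is missing is an individual stop at last assessment, death or first event. A reader might also infer from SAP 5.3.1 that pre-operative time is counted. That section defines a baseline value, not a start date, and the events are post-operative, so the documents do not support that reading.

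**Conclusion.** The point holds in limited form and the SAP should be changed. At the planning rate, the only Kaplan-Meier outputs named are ones that the study will rarely be able to report, while the useful output of the same curve is excluded. How rarely depends on follow-up and on the time point of the 5%. It ranges from under 0.01% with full follow-up to 7% in the tabulated patterns, and higher only with heavier early loss, a higher failure risk or outcome-related censoring.

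The person-time wording permits a 6-month rate that is too low by an amount set by how many patients have later notes. It does not establish that the two rates will differ. With near-complete 6-month follow-up the effect vanishes. The mismatch between SAP 5.8 and protocol 10.4 is a matter of record and changes no result.

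**What to change.** 1. In SAP 5.3.3, report Kaplan-Meier event-free probabilities at days 182 and 365 from operation, with numbers at risk at both days, in place of or beside the quantiles.
2. Label them as device failure/device-related re-intervention, supplementary to clinical success. State that they assume censoring at last chart contact is unrelated to outcome, that they would be too low if failures are charted more completely than well patients, and that day 365 rests on few patients at risk.
3. Amend the SAP 5.8 bullet to allow this, and list the Kaplan-Meier and incidence-rate analyses as additions to protocol 10.4.
4. Use one person-time for the crude rate and the Poisson offset: operation date to the earliest of last assessment, death, or day 182 (day 365 for the 12-month rate). Stop also at the first event when patients with a first event are the numerator. Name the numerator of each rate.

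The cost is SAP wording and a few table rows, because the failure, re-intervention and assessment dates are already planned in SAP 5.3.3 and 5.3.6.3. The drawback is a second estimate resting on few events. With full follow-up at 5%, 0.05 × 30 = 1.5 or 0.05 × 50 = 2.5 are expected, and none occur in 0.95^30 = 21% or 0.95^50 = 8% of studies, when it reads 100%. SAP 5.2 bars intervals, so the numbers at risk must show how little the day-365 figure rests on.

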**9.1.4 Retrospective chart review at 12 Months (365 days) Post-Operative (+ 30 days / -150)**

Given the retrospective study design, data will be collected from the medical chart to the extent it is available.

- |   |
|---|
| 
1. Collect the following retrospective data, to the extent it is available, from the subject's medical chart and complete the associated CRFs:
 
 
• Review study implant status 12 months post-operative for device related re-interventions and/or repair failure and assess clinical success.
 
• Obtain surgeon reported outcomes as defined in section 8.2.3 to the extent available at the 12 months follow-up.
 
• Collect Adverse Events and Device Deficiencies occurring from 6 months until 12 months follow-up.
 
• Collect concomitant medications or therapies.
 
 |
|---|

Study Protocol—Device	
Safety and Performance of MINITAC® Ti 2.0 Suture Anchor in Extremities	Number: MINI.PMCF.2018.11
	Version: 3.0, 20Aug19
	Page: Page 27 of 56

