3.5.3.2 Safety Endpoints

Safety endpoints include the collection of the following events from the subjects' medical record:

- All adverse events (AEs) and complications occurring from the time of subject enrollment until study termination or study completion including intra-operative adverse events and complications
- Device related re-intervention
- Device deficiencies (DDs)

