5.3 Statistical methods

5.3.1 General Analysis Definitions

Screening / Enrollment: For screening, only information available in the medical records will be reviewed. When all inclusion criteria and none of the exclusion criteria have been met for a subject and the informed consent process has been completed or a waiver of consent has been granted by the HREC/EC, the subject will be considered enrolled.

Baseline: Unless specified otherwise, the last non-missing value before study product installation/operation collected at the screening visit is considered as the baseline value.

Study Day:

Study Day = assessment date – study product installation/operation date + 1 for assessments post operation;

Study Day = assessment date – study product installation/operation date for assessments prior to operation;

All durations are calculated as the stop date minus the start date +1 unless otherwise specified.

End of Study: Due to the retrospective design of the study, end of the study is defined as the date when the last subject is documented on CRFs.

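### The Kaplan-Meier analysis in SAP 5.3.3 has no common end of follow-up, so one failure recorded after the 12-month review can produce an artefactual median and quartiles

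*SAP*

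**What the plan says.** **The analysis.** Under SAP 5.3.3, time from operation to first device failure and/or device-related re-intervention "will be analyzed using the Kaplan-Meier method to estimate median time and related 25th and 75th percentiles". The censoring rule is: "Patients without postoperative device failure or device related re-intervention will be censored at the latest date of assessment based on CRF data", or at death if that comes first. No latest day is given for events or for censoring.

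**The schedule.** The last review is at "12 months post operation (365 days + 30 / - 150 days"), that is, days 215 to 395. At that review Protocol 9.1.4 tells sites: "Collect Adverse Events and Device Deficiencies occurring from 6 months until 12 months follow-up".

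**The safety text.** SAP 3.5.3.2 collects adverse events and complications "occurring from the time of subject enrollment until study termination or study completion". SAP 5.3.6.2 and Protocol 8.2.3 use the same window. The re-intervention and device-deficiency items in those lists carry no window. SAP 5.3.1 adds that "end of the study is defined as the date when the last subject is documented on CRFs", which is a calendar date for the whole study.

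**Time since surgery.** Protocol 7.2 admits only subjects more than 12 months after surgery, and Protocol 7.4 screens from the earliest surgery forward. Charts can therefore run well past the 12-month review.

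**Related analyses.** The incidence rates in SAP 5.3.2 have bounded person-time (baseline to 6 months), and SAP 5.3.3 carries the method over to 12 months. SAP 5.8 says Kaplan-Meier will not be used for event rates. SAP 5.2 and 5.8 exclude confidence intervals, and SAP 5.3.4 plans no sensitivity analysis.

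**The concern.** Kaplan-Meier estimation needs the length of observation to be unrelated to the outcome. Here it may not be. A subject who fails late brings the late date with the failure. A subject who does not fail leaves the risk set at the last CRF assessment, which is the 12-month review if nothing later is recorded. After day 395 the risk set could then consist almost entirely of subjects who are about to fail.

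At stake are the median and the two quartiles, the only Kaplan-Meier results the SAP names. If about 5% of subjects fail, the curve stays near 0.95 and none of these percentiles can properly be reached within 12 months. Any median in the report would come from a thin tail, with no interval or sensitivity analysis beside it to show that it rests on one subject.

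**Working it through.** The plan gives no figure for this analysis, so there is none to reproduce.

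**Step 1: one late failure.** The estimator is S(t) = product of (1 − d/n) over event days, with d events among n at risk. Take one failure at day 500 (assumed) and k event-free subjects still at risk. With no earlier failure, S = 1 − 1/(k + 1) = k/(k + 1). The 25th percentile is reached when S ≤ 0.75, the median when S ≤ 0.50, and the 75th when S ≤ 0.25.

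| k | S after day 500 | Percentiles reached |
|---|---|---|
| 0 | 0 | 25th, 50th, 75th, all at day 500 |
| 1 | 0.50 | 25th, 50th |
| 2 | 0.667 | 25th |
| 3 | 0.75 | 25th |
| 4 | 0.80 | none |
| 10 | 0.909 | none |

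The k = 0 row holds for 30 or 50 subjects and for 0, 1 or 2 earlier failures, because the last factor is 1 − 1/1 = 0. Earlier failures lower the other rows slightly: two in 30 with k = 4 give 28/30 × 0.80 = 0.747, which just reaches the 25th percentile.

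**Step 2: chance of a recorded late failure.** This is 1 − (1 − q)^n, with q the probability per subject (assumed). For q = 0.5%, 1% and 2% it is 14%, 26% and 45% at n = 30, and 22%, 40% and 64% at n = 50.

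**Step 3: chance of a false median.** Simulation assumptions, none of them in the documents:
- 5% of subjects fail by day 365 (borrowed from the 95% success figure in SAP 5.7);
- event-free subjects are last assessed uniformly over days 215 to 395;
- late hazard is 0.5% to 2% per year;
- charts run on average 1 to 2 years past month 12.

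Ranges run from the mildest to the strongest setting.

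| Event-free subjects with a later CRF date | n = 30 | n = 50 |
|---|---|---|
| None | 11%–67% | 21%–84% |
| 20%, dates spread between day 395 and end of chart | 6%–42% | 6%–45% |
| 20%, date at end of chart | 3%–22% | 2%–17% |
| 50%, date at end of chart | 0.3%–4% | 0.3%–3% |
| All, date at end of chart | about 1% or less | about 1% or less |

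Repeat runs moved the limits of the first row by about 3 points. In that row the typical reported median is 18 to 26 months. The 25th percentile is more fragile: with 25% of event-free subjects carrying later dates, a false median appears in 1%–16% of studies and a false 25th percentile in 5%–48%.

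**Step 4: effect of a cut-off.** Cutting at day 395 turns the day-500 failure into a censored time. The curve then ends at 1.000, 0.967 or 0.933 for 0, 1 or 2 earlier failures in 30 (1.000, 0.980 or 0.960 in 50), and no percentile is reached. In simulation the median was reached in at most 0.3% of studies with a day-395 cut-off and under 0.1% with day 365. Day 395 is not a full cure. A failure at day 390, with everyone else last reviewed by day 385, again gives S = 0, and a day-365 cut-off removes that case. Numbers at risk still matter at day 365: in two constructed examples only 6 of 29 and 8 of 49 event-free subjects remained.

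**The case against.** Much of the text points to a 12-month end for each subject. The schedule tables mark end of study in the 12-month column. Protocol 7.8.1 aims for 12 months of data, the secondary objective runs to 12 months, and SAP 5.3.6.5 stops concomitant medication at the 12-month visit. On that reading a month-24 failure is never collected. The mechanism also needs two readings at once: late failures admitted, but event-free subjects held to the 12-month review. The SAP censors at the latest assessment on the CRF, which could be later. Finally, the 6- and 12-month proportions and the incidence rates do not depend on this curve, the study is descriptive, and the by-subject listing would show a lone late event.

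Most of this stands, and it rules out three stronger inferences:

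- A reader might infer that any late failure must take the curve to zero. It does so only when nobody else is at risk; step 1 shows how quickly the effect fades.
- A reader might infer that the study-completion window governs the Kaplan-Meier event. The text attaches it only to adverse events and complications.
- A reader might take 95% as the plan's event-free rate for this curve. It is a success rate, and SAP 5.3.2 also requires no inflammation, device-related adverse event or device deficiency.

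The objection does not remove the gap. The SAP never says that the 12-month end applies to this analysis, although it bounds the parallel rate analysis. The censoring rule as written allows follow-up to depend on outcome.

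**Conclusion.** The concern holds in conditional form. SAP 5.3.3 gives events and censoring no common end, and the documents conflict on when collection stops. A failure entered after the 12-month review can make the median and quartiles artefacts if few or no event-free subjects have later CRF dates. The probability cannot be fixed from the documents. Under the assumptions tried it runs from about 1% or less, when every event-free chart carries a date at its end, to over 80%, when none has a later date and late hazard and chart length are at their highest. The damage is confined to the Kaplan-Meier percentiles. It deserves correction before database lock because the rule as written can give a wrong result and a better one costs almost nothing.

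**What to change.** In SAP 5.3.3, state one administrative cut-off that applies equally to events and censoring. Day 365 is preferable; day 395 matches the visit window but leaves the small residual risk shown in step 4. Censor every subject still event-free at the earliest of last assessment, death or that day. Show numbers at risk, and report any percentile not reached as not estimable.

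Keep failures recorded after the cut-off in a listing, without a rate. Reconcile the stop-of-collection wording in Protocol 8.2.3 and 9.1.4 with SAP 3.5.3.2 and 5.3.6.2, and say which rule governs device failure and re-intervention.

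The analysis change is a short SAP addition and a line of code, with no new data. Aligning the protocol wording takes a clarification there too. The downside is small: failures after the cut-off, including those on days 366 to 395 if day 365 is used, leave the curve and appear only in the listing.
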